### **2.4 Risk-Benefit Assessment**

A patient with peanut allergy may or may not benefit from participating in this study. However, based upon the inhibition of IL-33 by the investigational product (IP) and pre-clinical study results, patients with peanut allergy may benefit. Participation in this study may help develop important scientific knowledge that could contribute to the development of a new medication and better comprehensive treatment of patients who suffer from AD, asthma, and food allergies.

ANB020 has been extensively tested in animals, and was found to be safe and well tolerated in a Phase I SAD study (ANB020-001) in healthy subjects. In animal studies, there were no ANB020 related adverse events (AEs) or abnormal ECG findings and the administration of ANB020 had no effect on hematology, coagulation, clinical chemistry, or urinalysis test results. In the SAD study, 64 healthy subjects were enrolled and dosed. The doses implemented in the SAD study were 10, 40, 100, and 300 mg SC and 40, 100, 300, 750 mg IV. No change in vital signs (BP, HR, ECG, or body temperature) was noted. Hematology parameters, such as erythrocytes, WBC, and platelet counts, were all within the normal range except for one subject in the 750 mg dose group. All others did not show any modification or trend related to ANB020 administration. Serum chemistry results were also all in the normal range. The most commonly reported TEAEs were upper respiratory tract infection (50% versus 48% in placebo and ANB020 group, respectively) and headache (32% versus 27% in placebo and ANB020 group, respectively) of mild to moderate intensity. No AEs were deemed by the Principal Investigator (PI) to be related to ANB020. Of all the AEs reported across all dose groups, 44% were reported as possibly related and 36% were reported as unrelated. One SAE of decreased neutrophils was reported in the 750 mg dose group which resolved without sequelae prior to study completion. No other observations of decreased neutrophils were observed. No dose dependent AEs were reported.

Although nothing in the testing of ANB020 to date indicates that an allergic reaction is likely; a reaction to any drug is possible. Some symptoms of allergic reactions are rash, wheezing or difficulty breathing, dizziness or fainting (also a possible outcome of a drop in BP), swelling around the mouth, throat or eyes, a fast pulse, or sweating.

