- c See [Table 7.1](#) for safety laboratory details (Virology, Quantiferon Gold® test, and drugs of abuse to be performed at screening only).
- d See [Section 18.0 \(Appendix 2\)](#) for schedule of PK collection time points.
- e See [Section 18.0 \(Appendix 2\)](#) for schedule of peanut challenge assay, biomarker cytokines, and whole blood for leukocytes collection time points. During screening the samples for ex vivo peanut antigen challenge, whole blood for leukocytes, and serum samples for cytokines should be collected prior to administration of BPCFC. If necessary, the sample for ex vivo peanut antigen challenge can be collected on Day 1(instead of Screening), prior to dosing. **Ex vivo Peanut challenge is for Stanford University only.**
- f ET visit will include all procedures to be done at EOS visit as well as any procedures that should be done at the next regularly scheduled visit. ET visit will be performed if the patient discontinues the study before EOS visit. If the patient completes all study visits and return to study center for EOS visit on Day 45, ET visit will not be applicable.
- g Leukocytes will be obtained as part of hematology safety laboratory panel at screening, Day 2, and Day 45/ET. On Day 5 and Day 15, whole blood samples for leukocytes will be collected separately as there is no safety laboratory assessment on Day 5 and Day 15.
- h Only conduct skin prick test and ImmunoCAP testing if these tests had not been performed within 8 weeks before screening.
- i For patients with a history of asthma, spirometry or peak flow will be obtained before starting the initial placebo challenge and again before starting the initial peanut challenge . See [Section 6.1.1](#).
- j Only applicable if the Investigator decides to complete the oral food challenge in 2 days. See [Section 6.1.1](#) and [7.1.3](#) for the instructions to record vital signs, physical examination, and clinical evaluations using the OFC Symptom Scoring Assessment Tool during BPCFC.
- k If the Investigator decides to complete the BPCFC on Day 15, the blood samples for leukocytes (whole blood), biomarker analysis (cytokines), and PK analysis should be collected on the following day (Day 16). The patient's vital signs, adverse events, if any, and concomitant medications will also be recorded on Day 16.

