Parameters derived from actual elapsed sample collection times [e.g., time to maximum observed concentration (t_{max})] will be reported in hours with 2 decimal places.

Apparent terminal rate constant (λ_z) will be reported with 4 decimal places.

For PK data, reporting of mean (arithmetic and geometric), SD, and median will carry 1 more significant figure than the source data. Minimum and maximum will carry the same number of significant figures as the source data. The bounds of any confidence intervals (CIs) will be reported with 2 decimals, and coefficient of variation (CV) will be reported as a percentage to 1 decimal place.

Extra measurements (such as unscheduled or repeat assessments) will not be included in the descriptive statistics, but will be included in subject listings. Pharmacokinetic summaries will be presented for all subjects in the PK analysis set as defined in [Section 5.5](#). Similarly, PD summaries will be presented for all subjects in the PD analysis set as defined in [Section 5.6](#). Data from subjects excluded from an analysis set will be included in the data listings, but not in the summaries.

Document: \\ieedc-nas01a\biosdata\AnaptysBio\ANB020\CYA74393\Biostatistics\Documentation\SAP\Final2018-02-07
Author: [REDACTED] Version Number: Final 1.0
Version Date: 07Feb2018

Template No: CS_TP_BS016 Revision 4
Effective Date: 01Apr2016

Reference: CS_WI_BS005

STATISTICAL ANALYSIS PLAN

AnaptysBio Inc
PROTOCOL ANB020-003
Page 17 of 36

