18.3. LABORATORY EVALUATIONS

Results from both the central and local laboratory will be included in the reporting. Central laboratory results will be reported for hematology, clinical chemistry and urinalysis. Local urine pregnancy test results will be reported as well. The actual and change from baseline values for each laboratory parameter will be summarized using descriptive statistics (n, mean, SD, median, and range) by treatment and all available visits.

The following summaries will be provided for laboratory data:

- o Incidence of abnormal values according to normal range criteria
- o Potential clinical significance of clinical laboratory assessments

A shift table will be presented of the potential shifts from baseline to the final measurement of values that are clinically relevantly high or low.

A listing of patients with abnormal values or clinically significant changes will be presented.

Document: \\ieedc-nas01a\biosdata\AnaptysBio\ANB020\CYA74393\Biostatistics\Documentation\SAP\Final2018-02-07
Author: [REDACTED] Version Number: Final 1.0
Version Date: 07Feb2018

Template No: CS_TP_BS016 Revision 4
Effective Date: 01Apr2016

Reference: CS_WI_BS005

STATISTICAL ANALYSIS PLAN

AnaptysBio Inc
PROTOCOL ANB020-003
Page 27 of 36

Hematology and clinical laboratory data will be reported in System International (SI) units.

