22. DATA NOT SUMMARIZED OR PRESENTED

The unscheduled visits will not be summarized, but listed.

Document: \\ieedc-nas01a\biosdata\AnaptysBio\ANB020\CYA74393\Biostatistics\Documentation\SAP\Final2018-02-07
Author: [REDACTED] Version Number: Final 1.0
Version Date: 07Feb2018

Template No: CS_TP_BS016 Revision 4
Effective Date: 01Apr2016

Reference: CS_WI_BS005

STATISTICAL ANALYSIS PLAN

AnaptysBio Inc
PROTOCOL ANB020-003
Page 33 of 36

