		-----	-----	-----	-----
Urinalysis Parameter 1	<Visits>	-----	-----	-----	-----

Urinalysis

Source: Listing 16 3 5 1

Note:

- N is the number of patients within each treatment group under Safety Analysis Set
- Percentages are based on number of patients within each treatment group under Safety Analysis Set (N)
- NCS – Not Clinically Significant, CS – Clinically Significant

Programming Note (not part of table): Use all relevant visits and parameters

Table 14 3 4 3
Laboratory Parameters – Safety Analysis Set

Laboratory Category Parameter	Visit	Statistics	Actual	ANB020	Placebo	Actual	Total	(N = XX)
				(N=XX)				
Hematology								
Parameter 1	Baseline	n	xx	-	xx	-	xx	-
		Mean (SD)	xx x (xx xx)	-	xx x (xx xx)	-	xx x (xx xx)	-
		Median	xx x	-	xx x	-	xx x	-
		Min, Max	xx, xx	-	xx, xx	-	xx, xx	-
	Day 1	n	xx	xx	xx	xx	xx	xx
		Mean (SD)	xx x (xx xx)					
		Median	xx x					
		Min, Max	xx, xx					

Day 45								
Parameter 2	-----	-----	-----	-----	-----	-----	-----	-----

Source: Listing 16 3 5 1

Note:

- N is the number of patients within each treatment group under Safety Analysis Set
- Baseline is defined as the last non-missing value before first dose of study medication

Programming Note (not part of table): Present all the parameters in Hematology, Clinical Chemistry, and Urinalysis
Provide appropriate descriptives for urinalysis Use all relevant visits

Table 14 3 4 4
Shifts from Baseline in Clinical Laboratory Results – Safety Analysis Set

Laboratory Category Parameter	Visit	Baseline Assessment	Post Baseline Assessments								
			ANB020 (N=XX)					Placebo (N=XX)			
			Low	Normal	High	Missing	Total	Low	Normal	High	Missing
Hematology											
Parameter 1	Day 1	Low	xx	xx	xx	xx	xx	xx	xx	xx	xx
		Normal	xx	xx	xx	xx	xx	xx	xx	xx	xx
		High	xx	xx	xx	xx	xx	xx	xx	xx	xx
		Missing	xx	xx	xx	xx	xx	xx	xx	xx	xx
		Total	xx	xx	xx	xx	xx	xx	xx	xx	xx
	Day 2										
	Parameter 2										

Source: Listing 16 3 5 1

Note:

- N is the number of patients within each treatment group under Safety Analysis Set
- Baseline is defined as the last non-missing value before first dose of study medication

Programming Note (not part of table): Present all the parameters in Hematology, Clinical Chemistry and Urinalysis Use all relevant visits

Document: \\ieedc-nas01a\biosdata\AnaptysBio\ANB020\CYA74393\Biostatistics\Documentation\SAP\Draft\2018-02-07
Author: [REDACTED]

Version Number: Draft 3.0
Version Date: 07Feb2018

Table 14 3 5 1
12-Lead ECG – Safety Analysis Set

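### SAP 18.3 and its table shell define the laboratory shift differently, and neither counts a patient whose only abnormal value is on an unscheduled draw

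*SAP*

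**What the plan says.** **Shift table, text.** SAP 18.3 describes one shift table, of "potential shifts from baseline to the final measurement of values that are clinically relevantly high or low". It does not name a visit.

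**Shift table, shell.** Table 14.3.4.4 in the table shells has a visit column running Day 1, Day 2 and onward, with low, normal, high and missing for each arm. Its programming note reads "Present all the parameters in Hematology, Clinical Chemistry and Urinalysis Use all relevant visits". (Table numbers here are those printed on the shells. The shells' contents list numbers the shift table 14.3.4.5.)

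**Other laboratory summaries.** The same SAP section has actual and change values "summarized using descriptive statistics (n, mean, SD, median, and range) by treatment and all available visits", and also plans "Incidence of abnormal values according to normal range criteria" and a clinical-significance summary. Shells 14.3.4.1 to 14.3.4.3 set these out by arm with a visit column.

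**Unscheduled values.** SAP 6 states: "Extra measurements (such as unscheduled or repeat assessments) will not be included in the descriptive statistics". SAP 22 states: "The unscheduled visits will not be summarized, but listed".

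**Sampling.** Protocol Table 4.1 schedules the safety laboratory at Screening, Days 1, 2, 14 and 45, and early termination. On the other two sampling days, "whole blood samples for leukocytes will be collected separately as there is no safety laboratory assessment on Day 5 and Day 15". SAP 20 summarizes those differentials by time point and treatment as pharmacodynamic data.

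**Prior experience.** Protocol 2.4 reports from the single-dose part of the Phase I study: "One SAE of decreased neutrophils was reported in the 750 mg dose group which resolved without sequelae prior to study completion".

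**The concern.** Clinical laboratory tests are among the primary safety endpoints (Protocol 9.4), and a shift table is where a reader usually looks for patients who moved from normal to abnormal. If it compares baseline only with the last value, it is blind to anything that goes abnormal and recovers. The one serious event that the protocol reports from Phase I was a laboratory change that recovered.

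The text and the shell also disagree, so the programmer has to choose. Whichever is chosen, results from unscheduled draws do not enter. Those are the samples an investigator would take to follow up a low count, and after Day 15 no scheduled blood count is taken until Day 45.

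**Working it through.** The plan states no figure to reproduce on this point, so most of the check is a side-by-side reading.

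**1. Which post-dose samples exist.** Protocol 6.0 requires assessments on the dosing day to precede the infusion unless otherwise noted, and Protocol Table 6.1 labels the Day 1 safety draw as pre-dose. Post-dose safety laboratory days are therefore 2, 14 and 45. Adding the separate leukocyte samples gives differentials on Days 2, 5, 14, 15 and 45.

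**2. The Day 1 row.** SAP 6.2 takes the nearest non-missing value before dosing as baseline. A pre-dose Day 1 result is that baseline, so the Day 1 row of Table 14.3.4.4 compares baseline with itself. Table 14.3.4.3 has the same Day 1 change row.

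**3. Where a low neutrophil count would appear by arm**, if baseline is normal and the count is normal at every other sample:

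| Low count seen on | Shift, 18.3 text | Shift, shell 14.3.4.4 | Tables 14.3.4.1–14.3.4.3 | PD table 14.5.1.1 | AE tables |
|---|---|---|---|---|---|
| Day 2 | no | yes | yes | yes | if an AE |
| Day 14 | no | yes | yes | no | if an AE |
| Day 5 or 15 | no | no | no | yes | if an AE |
| Day 45 | yes | yes | yes | yes | if an AE |
| Unscheduled draw only | no | no | no | no | if an AE |

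The last row is the gap: unless the value is recorded as an adverse event, no by-arm table holds it. The table rests on three readings:
- The incidence shell visible in the text is headed for the local laboratory, while 18.3 reports hematology centrally. I assume a central version is produced.
- The PD shell says only leukocytes. I follow SAP 20, which says differential counts.
- The sentence in SAP 6 on extra measurements stands among pharmacokinetic rules and could be read as limited to them. SAP 22 is general and settles the matter for unscheduled visits. For repeats at a scheduled visit, SAP 6 is the only rule.

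**4. No patient-level count.** None of the four laboratory shells has an any-time or worst-value row. The SAP uses that approach elsewhere: shell 14.3.5.2 counts QT values reached at any time during treatment, and SAP 18.1 counts an adverse event at its highest severity.

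**5. What a summary rule could recover (illustration).** Assume onset uniform over the 44 days from Day 1 to Day 45 and a fall lasting *d* days. A sample on day *s* meets the fall if onset lies between *s* − *d* and *s*. The share met is the length of the union of these intervals within Days 1 to 45, divided by 44.

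| Samples used | *d* = 7 | *d* = 14 |
|---|---|---|
| Day 45 only | 7/44 = 16% | 14/44 = 32% |
| Days 2, 14, 45 | (1 + 7 + 7)/44 = 34% | (13 + 14)/44 = 61% |
| Days 2, 5, 14, 15, 45 | (4 + 8 + 7)/44 = 43% | (14 + 14)/44 = 64% |

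The first line describes one table read alone. The plan's existing by-arm tables together already reach the third line. Falls met by no scheduled sample have onset on Days 5–7 or 15–38 for *d* = 7, which is (2 + 23)/44 = 57%. For *d* = 14 they have onset on Days 15–31, which is 16/44 = 36%. That remainder is a sampling gap, almost all of it between Days 15 and 45. A summary rule recovers only the part where an unscheduled sample was drawn, and the documents give no rate for such draws.

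**6. Weight of one patient.** The planned split is 20 × 3/4 = 15 and 20 × 1/4 = 5 (Protocol 6.2.2). One uncounted patient is 1/15 = 6.7% of the ANB020 arm or 1/5 = 20% of the placebo arm.

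**The case against.** A reader might infer that a repeat of the Phase I neutrophil event would be in no arm summary, or that the plan cannot show an event of that kind. The documents do not support this. A low count on Day 2 or 14 would appear as a visit minimum, in the low-value incidence and in the clinical-significance status, all by arm. Day 5 and 15 counts reach the pharmacodynamic table by arm.

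The Phase I event was also an SAE. Protocol 7.1.2 makes a laboratory abnormality judged clinically significant an adverse event, although one consistent with a current diagnosis may be documented otherwise. SAP 18.1 tabulates TEAEs and serious TEAEs by arm, and that route does not depend on a scheduled visit.

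Nor can the 16% and 32% in the working be read as the plan's detection rate. They describe a single table, on onset and duration assumptions that the documents do not supply.

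It can fairly be added that the study plans about 20 patients, makes no between-arm safety tests (SAP 18) and lists individual data, and that the prior signal was one subject at 750 mg against 300 mg here. All of this lowers the weight of the point.

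What the objection does not remove is the contradiction between text and shell, the Day 1 row, and the last row of the table in the working. The adverse event route depends on the investigator's judgement of clinical significance. The listing is also a weaker backstop than 18.3 suggests: 18.3 promises abnormal values or clinically significant changes, but Listing 16.2.8.1 is titled for clinically significant results only.

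**Conclusion.** The point holds as a minor one. SAP 18.3 and Table 14.3.4.4 give two incompatible definitions of one primary-safety table, and the shell treats a pre-dose visit as post-baseline. If the text is followed, the shift table uses one of three scheduled post-dose safety samples and shows a recovered abnormality as normal to normal. If the shell is followed, that is largely repaired. Under both, an abnormal value found only on an unscheduled draw and not recorded as an adverse event is counted in no by-arm table, and no laboratory table counts patients ever abnormal after dosing.

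How many patients this would affect cannot be estimated from the documents. It may be none. The conclusion assumes that the final measurement means Day 45 for completers (the early-termination sample for others) and that SAP 6 and 22 apply to laboratory counts as well as to means.

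**What to change.** - In SAP 18.3 and Table 14.3.4.4, use one definition: shift from baseline to the worst post-dose value, with the lowest and the highest value handled separately. Use every post-dose result, including unscheduled and repeat samples and, for leukocytes, the Day 5 and Day 15 differentials.
- State this as an exception to the exclusions in SAP 6 and 22.
- Remove Day 1 as a post-baseline visit from Table 14.3.4.4, and likewise from Table 14.3.4.3.
- Add an any-post-dose row to Table 14.3.4.2, so that each patient ever abnormal is counted once per parameter. The by-visit rows can stay.
- Align the title of Listing 16.2.8.1 with the 18.3 text.

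The cost is a change of SAP wording and one derivation, with no new data. The drawback is that worst-value tables also count isolated outliers, so abnormality counts rise slightly in both arms. A footnote can say so. The change does not close the Day 15 to Day 45 sampling gap.

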18.4. ECG EVALUATIONS

The following ECG parameters will be summarized:

- o Heart Rate (bpm)
- o PR Interval (msec)
- o QRS Interval (msec)
- o QT Interval (msec)
- o QTcB (msec) {based on Bazett formula}
- o QTcF (msec) {based on Fridericia formula}

The actual and change from baseline values for the above parameters will be summarized using descriptive statistics (n, mean, SD, median, and range) by treatment and all available visits.

The overall assessment of ECG will be summarized using frequency and percentage of the following indications:

- o Normal
- o Abnormal, Not Clinically Significant (ANCS)
- o Abnormal, Clinically Significant (ACS)

A listing of ECG parameters and of the overall assessment will be provided.

18.4.1. ECG SPECIFIC DERIVATION

Bazett's Correction (msec)

$$QTcB \text{ (msec)} = \frac{QT \text{ (ms)}}{\sqrt[3]{RR \text{ (ms)}/1000}}$$

Fridericia's Correction (msec)

$$QTcF \text{ (msec)} = \frac{QT \text{ (ms)}}{\sqrt[4]{RR \text{ (ms)}/1000}}$$

Document: \\ieedc-nas01a\biosdata\AnaptysBio\ANB020\CYA74393\Biostatistics\Documentation\SAP\Final2018-02-07
Author: [REDACTED] Version Number: Final 1.0
Version Date: 07Feb2018

Template No: CS_TP_BS016 Revision 4
Effective Date: 01Apr2016

Reference: CS_WI_BS005

STATISTICAL ANALYSIS PLAN

AnaptysBio Inc
PROTOCOL ANB020-003
Page 28 of 36

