#### **9.4.2 Vital Signs Measurements, Physical Findings, and Clinical Laboratory Evaluations**

Summaries and listings of data for vital signs, hematology, clinical chemistry, and urinalysis laboratory tests, ECGs and physical examination findings will be presented. Appropriate descriptive statistics will be summarized for the observed value at each scheduled assessment and for the corresponding change from baseline.

For hematology and clinical chemistry tests, listings of patient data will also flag up any abnormal or out-of-range values. Clinically significant changes in the laboratory test parameters will be summarized and listed. Hematology and clinical laboratory data will be reported in System International units.

For ECG variables, the QT correction factor will be based on both the Bazett and Fridericia formulae (QTcB and QTcF). Categorical summaries of absolute QT, QTcB and QTcF values and change from (baseline) values in QT, QTcB and QTcF values will be presented by treatment and visit.

Descriptive statistics will be used to present the safety outcomes including, physical examination results, weight, BMI, vital signs measurements, clinical laboratory test results, and ECG results. Change from baseline will also be summarized for vital signs measurements, clinical laboratory test results.

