3.3. CHANGES TO ANALYSIS FROM PROTOCOL

No changes from the analysis planned in the protocol were made.

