18.4.2. ECG MARKEDLY ABNORMAL CRITERIA

Absolute values of the QT interval will be classified as:

- >=450 msec
- >=480 msec
- >=500 msec

The change from Baseline of QT interval will be classified as:

- >30 msec increase from baseline
- >60 msec increase from baseline

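### SAP 18.4.1 prints the wrong root in both QT corrections, so QTcB and QTcF are wrong at every heart rate except 60 bpm and too low above it

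*SAP*

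**What the plan says.** The protocol names the two methods in section 9.4.2: "the QT correction factor will be based on both the Bazett and Fridericia formulae (QTcB and QTcF"). SAP 18.4 carries the same names into its list of ECG parameters: "QTcB (msec) {based on Bazett formula"} and "QTcF (msec) {based on Fridericia formula"}.

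SAP 18.4.1 then gives the formulas. Under the Bazett heading it has "QTcB \text{ (msec)} = \frac{QT \text{ (ms)}}{\sqrt[3]{RR \text{ (ms)}/1000" and under the Fridericia heading "QTcF \text{ (msec)} = \frac{QT \text{ (ms)}}{\sqrt[4]{RR \text{ (ms)}/1000" (closing braces omitted; the bracketed figure is the root index). So RR in seconds is taken to the cube root for QTcB and to the fourth root for QTcF.

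SAP 3.3 declares no departure from the protocol: "No changes from the analysis planned in the protocol were made". No other section of either document gives a QTc formula that would override 18.4.1.

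**The concern.** Both formulas contradict the names above them. Bazett's correction divides QT by the square root of RR in seconds, and Fridericia's divides it by the cube root. Each printed root index is one too high. The printed QTcB is therefore Fridericia's correction under Bazett's name, and the printed QTcF matches neither method.

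ECG is one of the primary safety endpoints (protocol synopsis and 9.4). Table shell 14.3.5.1 reports QTcB and QTcF by arm, with change from baseline. A formula that under-corrects at faster heart rates can hide QT prolongation in those rows. Because the size of the error depends on heart rate, a change in heart rate between visits also shows up as a spurious change in QTc.

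**Working it through.** **Inputs.** The printed exponents (1/3 and 1/4) come from SAP 18.4.1. The correct exponents (1/2 for Bazett, 1/3 for Fridericia, RR in seconds) are the definitions of the named methods; the documents do not restate them. The QT values and heart rates below are assumptions for illustration, since the documents give none. RR in ms is 60000 / heart rate. The SAP has no worked QTc value to reproduce.

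**Relative error.** Let r = RR/1000.

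- Printed QTcB / Bazett = r^(−1/3) / r^(−1/2) = r^(1/6)
- Printed QTcF / Fridericia = r^(−1/4) / r^(−1/3) = r^(1/12)

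Neither ratio depends on QT. Each equals 1 only when r = 1 (60 bpm), is below 1 above 60 bpm, and is above 1 below 60 bpm. At 100 bpm r = 0.6, which gives errors of −8.2% for QTcB and −4.2% for QTcF.

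**Values at an assumed QT of 360 ms** (ms; differences taken before rounding):

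| Heart rate | RR | QTcB printed | Bazett | Difference | QTcF printed | Fridericia | Difference |
|---|---|---|---|---|---|---|---|
| 50 | 1200 | 338.8 | 328.6 | +10.1 | 344.0 | 338.8 | +5.2 |
| 60 | 1000 | 360.0 | 360.0 | 0.0 | 360.0 | 360.0 | 0.0 |
| 70 | 857 | 379.0 | 388.8 | −9.9 | 374.1 | 379.0 | −4.8 |
| 80 | 750 | 396.2 | 415.7 | −19.5 | 386.8 | 396.2 | −9.4 |
| 90 | 667 | 412.1 | 440.9 | −28.8 | 398.4 | 412.1 | −13.7 |
| 100 | 600 | 426.8 | 464.8 | −37.9 | 409.0 | 426.8 | −17.8 |

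The printed QTcB column repeats the Fridericia column, as the algebra requires.

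**Effect on a cut-off.** At 100 bpm a true QTcF of 450 ms corresponds to QT = 450 × 0.6^(1/3) ≈ 380 ms. The printed formula reaches 450 only at QT = 450 × 0.6^(1/4) ≈ 396 ms. Likewise, for a QT of 400 ms at 80 bpm, Bazett gives 461.9 ms and the printed formula 440.3 ms, on opposite sides of 450.

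**Effect on change from baseline.**

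- Suppose true QTcF stays at 410 ms while heart rate goes from 60 to 90 bpm. The printed value at the second visit is 410 × (2/3)^(1/12) ≈ 396 ms, an apparent fall of about 14 ms where there was no change.
- Suppose true QTcF rises from 410 to 440 ms while heart rate goes from 60 to 80 bpm. The printed second value is 440 × 0.75^(1/12) ≈ 430 ms, so a 30 ms rise appears as about 20 ms.

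**Which outputs are touched.** The QTcB and QTcF rows of Table 14.3.5.1, with their changes from baseline, and ECG Listing 16.2.8.2 would carry the error. The categorical counts in SAP 18.4.2 and Table 14.3.5.2 would not, because the SAP applies its cut-offs to uncorrected QT: "Absolute values of the QT interval will be classified as" 450, 480 and 500 ms or more.

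**The case against.** The strongest objection is that the point rests on two small root indices in text converted from PDF, where small marks can be lost or misread. The intended methods are named correctly everywhere else, and the analysis program, which has not been seen, may use the right formulas. That caution stands, and the page image and program should be checked. It does not remove the point. A misreading would need two slips in the same direction: an index appearing on a root that normally shows none, and a 3 becoming a 4. The plain square root in the geometric CV formula of protocol 9.6.3 came through without an index.

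The second objection is that the consequence is limited, and this largely stands:

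- The SAP's threshold counts use raw QT. The cut-off examples above would matter only for the QTc categories in protocol 9.4.2, "Categorical summaries of absolute QT, QTcB and QTcF values and change from (baseline) values in QT, QTcB and QTcF values will be presented", which the SAP does not specify. That gap is a separate discrepancy.
- Table 14.3.5.1 also has a QTc row distinct from QTcB and QTcF, though its correction method is not stated. The investigator reviews each ECG, and the overall assessment is tabulated.
- ECGs are scheduled only at screening and at Day 45 or early termination, in about 20 patients, and safety data are not formally compared between arms.
- At resting rates near 70 bpm the errors are about 5 and 10 ms rather than the 18 and 38 ms seen at 100 bpm. Where heart rate is similar at both visits, most of the error cancels in change from baseline.

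These points limit the reach of the error, but they do not make the printed formulas right.

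**Conclusion.** The concern holds. A programmer following SAP 18.4.1 as printed would produce no Bazett value, would report Fridericia's correction under Bazett's label, and would report under Fridericia's label a quantity that is neither method. Both are wrong away from 60 bpm. At 70 to 100 bpm QTcB is 2.5% to 8.2% low and QTcF 1.3% to 4.2% low; at 50 bpm they are 3.1% and 1.5% high. The percentages follow from the exponents alone, and the millisecond figures depend on the assumed QT and heart rate.

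The damage is confined to the QTcB and QTcF summaries, their changes from baseline and the ECG listing. Efficacy and the SAP's raw-QT categories are unaffected. It should still be corrected before ECG results are reported, because it is a plain error in a primary safety derivation and runs against the protocol and the SAP's own labels. The one condition is that the signed SAP page shows the same root indices as the text reviewed here.

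**What to change.** - Compare section 18.4.1 of the signed SAP with the formulas quoted here. If the indices are as printed, correct them to QTcB = QT / (RR/1000)^(1/2) and QTcF = QT / (RR/1000)^(1/3), with QT and RR in ms.
- State how RR is obtained. Protocol 7.1.3 records heart rate, PR, QRS, QT and QTc but not RR. If RR is to be derived, write RR (ms) = 60000 / heart rate.
- Check the program behind Table 14.3.5.1 and Listing 16.2.8.2 against the corrected formulas, whatever the signed page shows, and rerun those outputs if it used the printed ones. A test record with QT 360 ms at 100 bpm should return QTcB 464.8 and QTcF 426.8 ms.
- If the QTcB and QTcF categories required by protocol 9.4.2 are produced, derive them from the corrected values.

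The cost is two formula corrections and a sentence on RR in the SAP, one program check and, if needed, a rerun of one table and one listing. No new data are required.
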